3.5 Duration of Follow Up

Due to the potential for late toxicities from pembrolizumab, patients will be followed for at least 1 year after their last dose of pembrolizumab or up to 2 years post-surgery for RFS whichever occurs last.

3.6 Randomization Procedures

This is a single-arm non-randomized trial. Additionally, this is an open-label trial; therefore, Merck, the investigator, and the patient will know the treatment administered. The trial is not designed to compare arms.

3.7 Study Timeline

3.7.1 Primary Completion

The study will reach primary completion, at the time the last participant has data collected for the primary objective to be measure. We estimate this occurring from the time the study opens to accrual.

3.7.2 Study Completion

The study will reach study completion 72 months from the time the study opens to accrual.

4 Study Drugs

4.1 Description, Supply and Storage of Investigational Drugs

4.1.1 Pembrolizumab

Details on the preparation and administration of pembrolizumab are provided in the Pharmacy Manual and package insert. Refer to the IB for additional information on pembrolizumab.

Classification

PD-L1 inhibitor, immunotherapy

Mechanism of Action

Pembrolizumab (MK-3475) is a potent humanized IgG4 mAb with high specificity of binding to the PD-1 receptor, thus inhibiting its interaction with PD-L1 and PD-L2. Based on preclinical *in vitro* data, pembrolizumab has high affinity and potent receptor blocking activity for PD-1. For more details see Section 1.2.1.1 and the IB.

Contraindications

Immunodeficiency, autoimmune diseases requiring treatment with disease modifying agents, corticosteroids or immunosuppressive drugs, active infections.

Availability

Pembrolizumab will be provided to patients enrolled on this study by Merck.

Handling, Storage, and Specific Accountability

The local country Merck personnel or designee will provide appropriate documentation that must be completed for drug accountability and return, or local discard and destruction if appropriate.

Phase 2, Pembrolizumab, Vactosertib

Where local discard and destruction is appropriate, the investigator is responsible for ensuring that a local discard/destruction procedure is documented.

The trial site is responsible for recording the lot number, manufacturer, and expiry date for any locally purchased product as per local guidelines unless otherwise instructed by Merck.

Clinical Supplies will be provided by Merck as summarized in Table 2.

Table 2 Product Descriptions

Product Name & Potency	Dosage Form
Pembrolizumab 25 mg/mL	Solution for Injection

Clinical Supplies Disclosure

This trial is open-label; therefore, the patient, the trial site personnel, Merck and/or designee are not blinded to treatment. Drug identity (name, strength) is included in the label text; random code/disclosure envelopes or lists are not provided.

4.1.2 Vactosertib

Refer to the IB for additional information on vactosertib.

Classification

Serine/threonine kinase inhibitor

Mechanism of Action

For more details see section 1.2.2 and the IB.

Contraindications

Vactosertib is predominately metabolized by CYP3A4. Because grapefruit and grapefruit juice are strong CYP3A4 inhibitors, these should be avoided in this study.

Description

The vactosertib film-coated tablets contain the following inactive ingredients: lactose monohydrate (Fastflo 316), microcrystalline cellulose (Avicel PH 102), crospovidone (Kollidon CL F), povidone Kollidon 30, magnesium stearate, and opadry white. The proposed clinical drug product vactosertib (50 mg, 100 mg and 200 mg film-coated tablets) is compressed from 10%w/w(50 mg), 40%w/w(100 mg, 200 mg) drug loaded common stock wet granulation.

Availability

Vactosertib will be provided to patients enrolled on this study by MedPacto.

Handling, Storage, and Specific Accountability

Clinical Supplies will be provided by MedPacto as summarized in Table 3.

Table 3 Product Descriptions

Product Name & Potency	Dosage Form
Vactosertib 50 mg	Film-coated tablets
Vactosertib 100 mg	Film-coated tablets
Vactosertib 200 mg	Film-coated tablets

Vactosertib tablets are packaged in tightly closed, white, opaque, HDPE bottles with a 1-g silica gel desiccant canister. The bottles are heat-induction sealed with a child-resistant cap. Based on the available laboratory stability data, vactosertib tablets should be stored at 15°C to 25°C (59°F to 77°F) and protected from light. Recent data indicate that 50 mg vactosertib remain stable up to 36 months, 100 mg and 200 mg vactosertib remain stable up to 9 months, respectively, under the same testing conditions as above. Stability test for a longer time period is underway: 50 mg, 100 mg and 200 mg vactosertib up to 60 months.

Clinical Supplies Disclosure

This trial is open-label; therefore, the patient, the trial site personnel, MedPacto and/or designee are not blinded to treatment. Drug identity (name, strength) is included in the label text; random code/disclosure envelopes or lists are not provided.

4.2 Drug Accountability

The Investigational Pharmacist will manage drug accountability records.

The investigator or designee must confirm appropriate temperature conditions have been maintained during transit for all study treatment received and any discrepancies are reported and resolved before use of the study treatment.

Only patients enrolled in the study may receive study treatment and only authorized site staff may supply or administer study treatment. All study treatments must be stored in a secure, environmentally controlled, and monitored (manual or automated) area in accordance with the labeled storage conditions with access limited to the investigator and authorized site staff.

The investigator, institution, or the head of the medical institution (where applicable) is responsible for study treatment accountability, reconciliation, and record maintenance (i.e., receipt, reconciliation, and final disposition records).

The study site is responsible for recording the lot number, manufacturer, and expiry date for any locally purchased product (if applicable) as per local guidelines unless otherwise instructed by Merck.

The investigator shall take responsibility for and shall take all steps to maintain appropriate records and ensure appropriate supply, storage, handling, distribution and usage of study treatments in accordance with the protocol and any applicable laws and regulations.

4.3 Drug Ordering

UCSF will obtain pembrolizumab directly from Merck as study supply. Commercial drug will be supplied locally. UCSF will obtain Vactosertib directly from MedPacto as study supply.

4.4 Packaging and Labeling of Study Drugs

Drugs will be packaged and affixed with a clinical label per UCSF institutional standards, adhering to applicable local and federal laws.

5 Treatment Plan

5.1 Dosage and Administration

Trial treatment should be administered at the time points specified in the Trial Flow Charts (section 6.2). The treatment to be used in this trial is outlined in Table 4 and Table 5. On Day 1 of each cycle, administer vactosertib after the subject completes their pembrolizumab infusion. Vactosertib may be administered as soon as the pembrolizumab infusion is completed. Vactosertib and pembrolizumab may be administered without regard to meals.

Table 4 Main Trial Treatment

Drug	Dose/ Potency	Dose Frequency	Route of Administration	Regimen/ Treatment Period	Use
Pembrolizumab	200 mg	Once	IV infusion	C1D1	Experimental
Vactosertib	200 mg	QD, 5 days per week	PO	C1D1 through C1D14	Experimental

Abbreviation: IV = intravenous, PO = per os, C = cycle, D = day, QD = once a day

Table 5 Optional Adjuvant Treatment Cohort

Drug	Dose/ Potency	Dose Frequency	Route of Administration	Regimen/ Treatment Period	Use
Pembrolizumab	400 mg	Q6W	IV infusion	Up to 8 cycles	Experimental
Vactosertib	200 mg	Cycle 1: QD, 5 days per week Cycles 2+: BID, 5 days per week	PO	Up to 8 cycles	Experimental

Abbreviation: IV = intravenous, PO = per os, C = cycle, D = day, Q6W = every 6 weeks, QD = once a day, BID = twice a day

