Study Drugs	
Neoadjuvant pembrolizumab will be administered at a fixed dose of 200 mg (IV) for 1 cycle plus 200 mg vactosertib (PO QD, 5 days per week x 2 weeks).
 
Adjuvant pembrolizumab (400 mg IV) + vactosertib (200 mg PO QD Cycle 1, 5 days per week, Cycles 2 and beyond 200 mg BID, 5 days per week) will be administered for up to eight 6-week cycles.

Phase 2, Pembrolizumab, Vactosertib

Safety Assessments	Safety assessments will include adverse events, clinical laboratory evaluations, and vital signs.
Efficacy Assessments	Objective response rate, pathologic response rate, R0 resection rate, and 1-year and 2-year RFS.
Unique Aspects of this Study	This is the first study to evaluate the safety and efficacy of pembrolizumab plus vactosertib following FOLFOX chemotherapy in patients with metastatic CRC undergoing liver resection with curative intent. Biopsy of a liver metastasis prior to administering pembrolizumab plus vactosertib and resection of the liver metastases following 1 cycle of pembrolizumab plus vactosertib will enable extensive scientific correlatives.

Study Schema

The above timeline is approximate with further guidelines below:

- A screening computed tomography (CT) chest/abdomen/pelvis with intravenous (IV) contrast must be performed and reviewed to confirm candidacy for hepatic resection prior to study entry.
- If chemotherapy is a direct lead-in to study enrollment, then liver resection surgery should be performed within 4-6 weeks of the final chemotherapy administration. During this 4-6 week window, 1 cycle of pembrolizumab plus vactosertib will be administered approximately 2 weeks (minimum 1 week) after the last dose of chemotherapy, and surgery will occur approximately 2 weeks (minimum 1 week) after C1D1.
- Labs, including liver function testing will be performed after C1D1, as close to surgery as possible.

Phase 2, Pembrolizumab, Vactosertib

- In the event that the surgery is canceled, and the first liver biopsy yielded adequate tumor material, a second liver biopsy will be requested (same lesion as the first biopsy preferred).
- Participants will be followed for up to 2 years after surgery or will be offered optional adjuvant treatment (described below).

Optional Adjuvant Treatment

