Based on the available tolerability data from 11 patients enrolled as of March 5, 2021, a decision was made to decrease the vactosertib dose from 300 mg BID to either 200 mg BID or 200 mg QD. Dose adjustment or withdrawal was required in 4 out of 11 patients and 2 Gr 3 events (acute hepatitis and skin rash) were considered to be related to the enhanced immune response to the study treatment. This reduced tolerability was unexpected as vactosertib 300 mg BID with pembrolizumab had shown acceptable tolerability in metastatic colorectal cancer patients in MP-VAC-204. The differences in tolerability between the two studies may be attributed to differences in the host immune status and prior exposures to cytotoxic chemotherapy. Subjects in MP-VAC-204 study had experienced 4 lines (median) of prior chemotherapy. Vactosertib 200 mg showed effective decrease in TGF- β downstream markers including phospho-SMAD, PAI-1, CTGF and PDGF.

In a mouse model, vactosertib 25 mg/kg, equivalent to human dose of approximately 120 mg QD, exerted antitumor activity when combined with anti-PD-1 treatment.

Arm 1 will evaluate the vactosertib dose escalation strategy. Vactosertib 200 mg QD will be administered with pembrolizumab during the 1st Cycle. If no significant drug-related toxicity is observed, vactosertib 200 mg BID will be administered with pembrolizumab during subsequent cycles. This will allow patients to develop tolerability. Such dose-escalation strategy based on tolerability has been successfully tested in other trials [Bekaii-Saab, T.S., et al., The Lancet Oncology, 2019]. Set dose of vactosertib 200 mg QD with pembrolizumab will be evaluated in Arm 2.

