1.3.2 Rationale for Dose Regimen

The planned dose of pembrolizumab for this study is 200 mg (IV) for 1 neoadjuvant cycle and 400 mg (IV) for up to eight 6-week adjuvant cycles (optional). The pembrolizumab doses used in this trial have been demonstrated to be well tolerated in earlier clinical trials.

The planned dose of vactosertib for this study is 200 mg PO QD, 5 days per week for 2 weeks during the neoadjuvant treatment period, and 200 mg PO QD, 5 days per week for 6 weeks (1 cycle) and depending on tolerability, patients will receive 200 mg PO BID, 5 days per week for up to 42 weeks (7 cycles) during the optional adjuvant treatment period. The vactosertib dosing regimen used in this trial has been demonstrated to be well tolerated in the ongoing early phase clinical trials.

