5.1.2 Vactosertib

Vactosertib will be administered once daily at 200 mg PO for 5 days followed by a 2-day resting period (5 days on/2 days off) for two weeks during the neoadjuvant treatment phase.

During the optional adjuvant treatment phase, vactosertib will be administered once daily at 200 mg PO (dose level -1) for 5 days followed by a 2-day resting period during Cycle 1. If no significant drug-related toxicities are observed, vactosertib will be administered twice daily at 200 mg PO (dose level 0) for 5 days followed by a 2-day resting period (5 days on/2 days off) for up to 8 cycles.

Please see Section 5.2, Dose Modifications and Dosing Delays for additional details.

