5.2 Dose Modifications and Dosing Delays

Dose modification guidelines for pembrolizumab-related AEs during the adjuvant period are provided in Table 7. Dose modification guidelines for pembrolizumab-related AEs during the neoadjuvant period do not apply as only a single dose of pembrolizumab will be administered.

Vactosertib dose reduction based on treatment-related adverse events observed is permitted.

According to the dose levels in Table 6, participants who receive vactosertib below the initially assigned treatment level (200 mg QD or BID) due to vactosertib-related AEs, will have the option to re-escalate to the assigned vactosertib dose if AE(s) resolves to baseline and does not recur for at least 3 consecutive weeks (one treatment cycle).

For the optional adjuvant treatment phase, participants who experience the following drug-related toxicities may escalate to dose level 0 based on the judgement of the investigator:

- Grade 1 or 2 Hematologic Toxicity
- Grade 1 non-hematologic toxicity and/or other drug related toxicities.
- Grade 1 ALT or AST elevation possibly related with total bilirubin <2x ULN

If a Grade 2 or lower vactosertib treatment-related toxicity is experienced but not specified, above dose escalation could be considered after discussions with MedPacto.

If a participant experiences several adverse events and there are conflicting recommendations, the investigator should use the recommended dose adjustment that reduces the dose to the lowest level or if warranted, discontinues therapy.

Table 6 Vactosertib Dose Modification

Neoadjuvant Treatment Phase		Optional Adjuvant Treatment Phase	
Treatment Level	Vactosertib Dose	Treatment Level	Vactosertib Dose
0	200 mg QD	0	200 mg BID
-1	100 mg QD	-1	200 mg QD
-2	100 mg QD	-2	100 mg QD

Vactosertib dose can be reduced to manage a treatment related AE as indicated in Table 9.

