8.1.1 Study Design

This is a single-site, single-arm, open-label Phase 2 clinical trial of pembrolizumab + vactosertib in patients with CRC with resectable hepatic metastases.

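### The rule for raising adjuvant vactosertib to twice daily from Cycle 2 is unconditional in Table 5 and the abstract but depends on Cycle 1 tolerability in sections 5.1.2 and 1.3.2, and section 1.2.2.3 describes dose arms that this single-arm trial does not define

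*Combined protocol and SAP*

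**What the plan says.** The abstract's Study Drugs entry gives adjuvant vactosertib as 200 mg once daily in Cycle 1 and then "Cycles 2 and beyond 200 mg BID, 5 days per week) will be administered for up to eight 6-week cycles". Table 5 in section 5.1 lists the same schedule: once daily in Cycle 1, then "Cycles 2+: BID, 5 days per week". Neither place attaches a condition or a footnote to the increase.

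Two other places do. Section 5.1.2 reads "If no significant drug-related toxicities are observed, vactosertib will be administered twice daily at 200 mg PO (dose level 0"), with a length of up to 8 cycles, and then refers the reader to section 5.2. Section 1.3.2 describes one six-week cycle at once daily, after which "depending on tolerability, patients will receive 200 mg PO BID, 5 days per week for up to 42 weeks (7 cycles").

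Section 5.2 adds that adjuvant participants with certain listed low-grade toxicities "may escalate to dose level 0 based on the judgement of the investigator". Table 6 labels twice daily as level 0 and once daily as level -1 in the adjuvant phase.

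Section 1.2.2.3, a background section, describes in the future tense an Arm 1 that starts at 200 mg once daily and moves to twice daily if there is no significant toxicity. It then says "Set dose of vactosertib 200 mg QD with pembrolizumab will be evaluated in Arm 2". Section 8.1.1 states "This is a single-site, single-arm, open-label Phase 2 clinical trial"; sections 3.1 and 3.6 also describe a single arm.

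**The concern.** Whether a patient's dose is raised after Cycle 1 is a safety decision, and the protocol should give one answer to it. Section 5.1 names Tables 4 and 5 as the place where the trial treatment is set out, so Table 5 is operative text. Footnote f to Table 11 gives no daily frequency and sends the reader back to section 5.1, which holds both the unconditional and the conditional wording.

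Someone working from Table 5 or the abstract would plan the increase for every patient who reaches Cycle 2. Someone working from 5.1.2 would first ask whether there had been a significant drug-related toxicity, a term that 5.1.2 does not define.

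The Arm text raises a different question. It resembles this trial's adjuvant schedule closely enough to be taken as part of it, yet nothing else in the protocol defines arms by vactosertib dose.

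**Working it through.** **Inputs.** 200 mg per dose, 5 dosing days per week (Table 5); six-week cycles, at most eight (abstract, sections 3.4 and 6.1.6.2, Table 5); up to 42 weeks or 7 cycles of twice-daily dosing (section 1.3.2).

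**1. The plan's own figure.** 7 cycles × 6 weeks = 42 weeks, which reproduces section 1.3.2. One once-daily cycle plus seven twice-daily cycles is 1 + 7 = 8, which fits the cap.

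**2. Planned dose.** Once daily: 1 × 200 = 200 mg per dosing day. Twice daily: 2 × 200 = 400 mg. Ratio 400 / 200 = 2.00. With 5 × 6 = 30 dosing days per cycle, this is 6,000 mg against 12,000 mg per cycle.

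**3. The texts applied to the same patient at the start of Cycle 2.**

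| Cycle 1 experience | Table 5 or abstract alone | Section 5.1.2 | Section 5.2 and Table 9 |
|---|---|---|---|
| No drug-related toxicity | Twice daily | Twice daily | No restriction |
| Toxicity on the 5.2 list | Twice daily | Depends on whether it counts as significant | May escalate, at the investigator's judgement |
| Significant drug-related toxicity | Twice daily | Condition for the increase not met | Action by grade: continue, withhold, reduce or discontinue |

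The first row shows no difference. In the second, an increase that Table 5 simply lists becomes discretionary under 5.2. In the third, Table 5 alone and 5.1.2 part by the factor of 2.00 from step 2, if the patient otherwise stays at once daily.

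**4. Length of twice-daily dosing.** Read literally, 5.1.2 gives one once-daily cycle and then up to eight twice-daily cycles: 1 + 8 = 9 cycles, or 9 × 6 = 54 weeks. The cap is 8 × 6 = 48 weeks. Read as running through Cycle 8, it gives seven twice-daily cycles and agrees with 1.3.2.

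**5. The Arm text.** Section 1.2.2.3 first reports MP-VAC-204 (17 + 33 = 50 patients). It then reports tolerability in 11 patients, a decision to lower vactosertib from 300 mg twice daily, and a contrast between two studies. MP-VAC-204 is one of the two; the other, which supplied the 11 patients, is not named. The Arm sentences follow without naming a study and without mentioning adjuvant treatment.

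**The case against.** The best defence is that Table 5 outlines the regimen and 5.1.2, in the same section, supplies the detail. Table 5 does not say that every patient escalates. Section 5.1.2 states the condition and points to 5.2, section 1.3.2 agrees, and Table 9 governs dosing after toxicity by grade. Much of this stands: an investigator who reads all of section 5 would probably not raise the dose automatically after a serious Cycle 1 event. What remains is that Table 5 is named as setting out the treatment and carries neither the condition nor a pointer to it, and the abstract repeats the omission.

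A reader might go further in four ways that the documents do not support.

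- **That Arm 2 is a third regimen in this trial.** It appears once, in background text, beside an unnamed study. No section gives an allocation rule or sample size for it. The mention in 5.2 of an assigned level of once or twice daily need not be a trace of it, because level 0 in Table 6 is once daily in the neoadjuvant phase and twice daily in the adjuvant phase.
- **That exposure differs nearly two-fold over the whole course.** Eight once-daily cycles are 8 × 6,000 = 48,000 mg; once daily then seven twice-daily cycles are 6,000 + 7 × 12,000 = 90,000 mg; the ratio is 1.875. This is planned dose, since no pharmacokinetic exposure can be derived. As a gap between written regimens it needs Arm 2 to be operative. Otherwise it compares a patient who never escalates with one who escalates fully, both completing eight cycles; over two cycles the ratio is 18,000 / 12,000 = 1.50.
- **That 5.1.2 extends treatment to nine cycles.** The eight-cycle cap is repeated in several sections, so this is most likely loose wording.
- **That the adjuvant summaries wrongly pool two regimens.** Titration by tolerability is one regimen, and section 8.4.3 plans descriptive statistics only. A split by dose received would itself be determined partly by Cycle 1 toxicity. Such a table is a preference, not a correction.

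**Conclusion.** The inconsistency holds, in a limited form. Operative text gives two statements of the Cycle 2 rule, one unconditional and one conditional, and they diverge for a patient with significant drug-related toxicity in Cycle 1. The size is a factor of two in planned daily dose from Cycle 2, on the assumption that Table 5 is read alone and that the patient would otherwise remain at 200 mg once daily. For a patient who tolerates Cycle 1 it is zero.

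The Arm text is a separate defect of attribution: the documents do not show whether it describes this trial or another. The seven-versus-eight mismatch is minor.

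None of this reaches the primary endpoint, which section 2.2 measures from before treatment to surgery, ahead of any adjuvant dosing. The documents do not settle which Cycle 2 rule is intended, and this review takes no position on it.

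**What to change.** Reconcile the abstract, Table 5 and sections 1.3.2, 5.1.2 and 5.2 to one rule for vactosertib from adjuvant Cycle 2 and one stated length of twice-daily dosing. State the rule the same way in the abstract and Table 5, each with a pointer to section 5.2. In section 1.2.2.3, name the study to which the two arms and the 11 patients belong, or remove the Arm text. The sponsor decides which rule is intended.

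The cost is wording in six places within one amendment. Sample size, the primary analysis and data collection do not change.
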